11.9 Duration of Hospitalization

Duration of hospitalization (days) will be defined in two ways:

- (1) The interval from the subject's date/time of hospital admission to the date/time the subject is discharged from the hospital (Hospitalization dataset: AEHO). If a subject is

hospitalized multiple times, then all hospitalizations will be added together to calculate the duration of hospitalization.

(2) The interval from the subject's date/time of hospital admission after study drug administration to the date/time the subject is discharged from hospital (Hospitalization dataset: AEHO). If a subject is hospitalized multiple times, then all hospitalizations will be added together to calculate the duration of hospitalization.

Those subjects that were not admitted to hospital or have no documentation of being discharged from the hospital will be censored for time to event analysis and will be imputed as the highest or lowest score for purposes of continuous analysis.

The same censoring/imputation rules as outlined above for ICU will be followed:

- (1) If subjects do not have a documented admittance into the hospital, the duration of hospitalization will be censored at Day 1.
- (2) If subjects are in the hospital through the entire follow-up phase, then the duration of hospitalization will be censored at the end of study date (maximum of 90 days).
- (3) If subjects die while in the hospital, then the duration of hospitalization will be censored at the date of death.
- (4) If subjects withdraw from study (any reason) while in the hospital, then duration of hospitalization will be censored at the date of study withdrawal.
- (5) If subjects are in hospital at the time of database lock and analysis (unlikely, but possible), the duration of hospitalization will be censored on the date of database lock.

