11.5 Time on Supplemental Oxygen or Mechanical Ventilation

The total time (days) on respiratory/ventilator (mechanical) support will be taken from the Respiratory/Ventilator eCRF page (dataset: QS1). The time will be calculated from the date/time that the subject required respiratory/ventilator support (eCRF checked “Yes” for this question) to the date/time that the subject did not need respiratory/ventilator support (eCRF checked “No” for this question). If a subject had multiple occurrences of needing mechanical support, then these times will be summed together.

Time on mechanical ventilation will be defined in two ways:

- (1) The interval from the subject’s date/time of the original mechanical ventilation collected (could be prior to study drug administration) to the date/time the subject is off mechanical ventilation. If a subject had multiple occurrences of needing mechanical support, then these times will be summed together.
- (2) The interval from the subject’s date/time of mechanical ventilation after study drug administration to the date/time the subject is off mechanical ventilation. If a subject had multiple occurrences of needing mechanical support, then these times will be summed together.

The censoring/imputation rules as defined above will be followed.

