11.7 Days in ICU and Time to Discharge

Duration in the ICU (days) will be defined in two ways:

- (1) The interval from the subject’s date/time of ICU admission to the date/time the subject is discharged from the ICU (Hospitalization dataset: AEHO). If a subject is admitted to the ICU multiple times, then all ICU visits will be added together to calculate the duration in ICU.
- (2) The interval from the subject’s date/time of ICU admission after study drug administration to the date/time the subject is discharged from the ICU (Hospitalization dataset: AEHO). If a subject was admitted to the ICU multiple times, then all ICU visits will be added together to calculate the duration in ICU.

Those subjects that were not admitted to the ICU or have no documentation of being discharged from the ICU will be censored for time to event analysis and will be imputed as the highest or lowest score for purposes of continuous outcome analysis.

The following censoring/ imputation rules will be followed:

- (1) If subjects do not have a documented admittance into the ICU, the duration in ICU will be censored at Day 1, or an imputed score of zero.
- (2) If subjects are in ICU through the entire follow-up phase, then the duration in ICU will be censored at the end of study date (maximum of 90 days), or imputed as the days in the study.
- (3) If subjects die while in ICU, then the duration in ICU will be censored at the date of death, or imputed as the days until death.
- (4) If subjects withdraw from study (any reason) while in the ICU, then duration in ICU will be censored at the date of study withdrawal or imputed as the number of days until withdrawal.
- (5) If subjects are in ICU at the time of database lock and analysis (unlikely, but possible), the duration in ICU will be censored on the date of database lock or imputed as the number of days until database lock.

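### Neither definition of duration in SAP 11.7 or 11.9 gives the declared post-infusion days in ICU or in hospital when the stay is already open at infusion

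*SAP*

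**What the plan says.** SAP 3.2 and Protocol 3 list, among twelve endpoints, days in ICU and days hospitalized. Both are counted from start of treatment and limited to 90 days.

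SAP 11.7 states: "Duration in the ICU (days) will be defined in two ways". SAP 11.9 uses the same construction for hospital stays. In both sections:

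- Definition (1) runs from admission to discharge, summed over stays.
- Definition (2) runs, for the ICU, from "ICU admission after study drug administration to the date/time the subject is discharged from the ICU" and, for the hospital, from "hospital admission after study drug administration to the date/time the subject is discharged from hospital", again summed over stays.

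Neither section says which definition is the main one, and the default analysis in SAP 11 does not choose between them.

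SAP 11.7 then gives rules for incomplete stays. A subject never in the ICU falls under rule (1): "the duration in ICU will be censored at Day 1, or an imputed score of zero". A subject in the ICU throughout follow-up falls under rule (2): "censored at the end of study date (maximum of 90 days), or imputed as the days in the study". For death in the ICU, rule (3) reads "censored at the date of death, or imputed as the days until death". Rules (4) and (5) treat withdrawal and database lock in the same way. SAP 11.9 says it carries these rules over, but its list gives only the censoring dates.

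SAP 11.8 takes the time from first IP administration to hospital discharge. Protocol 6.4 has the product given to inpatients.

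**The concern.** The declared quantity is the part of each stay that falls after infusion. Definition (1) is too long by whatever part of the stay came before infusion. Definition (2) ties the phrase about study drug to the admission rather than to the days counted, and no sentence in either section cuts an open stay at the infusion date. A programmer who follows it exactly skips any stay that began before dosing. For the hospital endpoint that is the index stay of every subject dosed as an inpatient.

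Two programmers could therefore derive different values for the same subject from the same text. With no main definition named, the choice also stays open until someone makes it. That should not happen after unblinding.

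**Working it through.** No figure in the plan can be reproduced here. The check applies each definition to example stays.

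**Inputs.** The declared origin and 90-day limit come from SAP 3.2, the definitions and rules from SAP 11.7 to 11.9, and inpatient dosing from Protocol 6.4. All stay dates below are assumptions. Infusion is on Day 1, so Day d is d − 1 elapsed days after infusion.

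**Formulas.**

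- Endpoint: sum over stays of max(0, min(end of stay, 90) − max(admission, 0)), in elapsed days from infusion.
- Definition (1): sum of (end of stay − admission).
- Definition (2): the same sum, restricted to stays with admission after infusion.

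Where a stay ends in death or withdrawal, that date closes it.

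| Case (assumed dates) | Endpoint | Def. (1) | Def. (2) as worded | Other SAP text |
|---|---|---|---|---|
| A. Hospital: admitted 4 days before infusion, discharged Day 12 | 12 − 1 = 11 | 11 + 4 = 15 | 0 | 11.8: 11 |
| B. As A, readmitted Day 20 to Day 23 | 11 + 3 = 14 | 15 + 3 = 18 | 3 | 11.8: 11 (first discharge) or 22 (last) |
| C. ICU: entered 2 days before infusion, left Day 8, back Day 20 to Day 23 | 7 + 3 = 10 | 10 + 2 = 12 | 3 | – |
| D. ICU: Day 3 to Day 8 | 8 − 3 = 5 | 5 | 5 | – |
| E. ICU: entered 2 days before infusion, never left, followed at least 90 days | 90 | – | 0 | 11.7 rule (2): up to 90 |
| F. ICU: entered 2 days before infusion, died there Day 15 | 15 − 1 = 14 | 14 + 2 = 16 | 0 | 11.7 rule (3): 14 from infusion |
| G. Hospital: admitted 4 days before infusion, withdrew in hospital Day 10 | 10 − 1 = 9 | 9 + 4 = 13 | 0 | – |
| H. ICU: entered Day 10, died there Day 15 | 15 − 10 = 5 | 5 | 5 | 11.7 rule (3): 14 from infusion |
| I. ICU: as C, but died there Day 23 | 7 + 3 = 10 | 12 | 3 | 11.7 rule (3): 22 from infusion |

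**Reading the table.**

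- A, B, C and G: for a stay open at infusion, neither definition returns the endpoint.
- D: for an ICU stay that begins after infusion, both definitions are right.
- E and F: the imputation rules of 11.7 contradict definition (2) as worded.
- H and I: rule (3) names no origin. Counted from infusion, it also differs from the days actually spent in the ICU, even where definition (2) is right. Correcting the definition alone would leave this conflict in place.

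**Check of the repair.** Closing each stay at the earliest of discharge, death, withdrawal, end of study, database lock and 90 elapsed days, and starting it at the later of admission and infusion, gives 11, 14, 10, 5, 90, 14, 9, 5 and 10 for A to I. It gives 0 for a subject never in the ICU.

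**Related point in 11.6.** That section takes ICU dates from the last hospitalization, while SAP 3.2 declares the first ICU discharge. In case C, if the second ICU stay falls in a readmission, the first discharge is at 8 − 1 = 7 days and the last at 23 − 1 = 22.

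**The case against.** The strongest reply is that the intent is clear from context:

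- SAP 3.2 itself fixes the origin and the limit.
- Rule (1) in both sections refers to Day 1, the infusion day, and rule (2) in both sets a maximum of 90 days.
- SAP 11.5 uses the same pair of definitions for ventilation. In the first, the start "could be prior to study drug administration". The second runs from "date/time of mechanical ventilation after study drug administration to the date/time the subject is off mechanical ventilation", which reads naturally as the post-infusion part.
- SAP 11.8 already yields hospital days from first IP administration for anyone not readmitted.

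Most of this stands, and it limits the practical exposure. It does not remove the error. The rules cover only subjects never admitted or not discharged, 11.8 does not sum readmissions (case B), and 11.6, the corresponding ICU section, gives time to discharge and not summed days.

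Three stronger readings are tempting, and the documents do not support them.

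- *The endpoints will be computed wrongly, with 0 hospital days for nearly everyone.* The point concerns the wording. The surrounding text makes that outcome unlikely.
- *Definition (1) biases the comparison.* The added days precede treatment, so they do not favour either arm. The result is simply not the declared quantity.
- *Every ICU stay is affected because Protocol 6.6 says all patients will be managed in an ICU.* That sentence concerns the availability of treatment for allergic reactions. Rule (1) of SAP 11.7 provides for subjects never in the ICU, and Protocol 5.2 excludes intubated patients.

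**Conclusion.** Wrong as written, and of low to moderate importance. For a stay open at infusion, neither definition returns the declared endpoint: in case A the values are 15 and 0 against 11. For the hospital endpoint this rests only on dosing in an inpatient setting. What 11.8 does not recover is confined to readmitted subjects. For the ICU endpoint it depends on how many stays were open at infusion. The documents give neither that number nor the readmission rate, so the effect on the trial's results cannot be sized. The day counts above rest on assumed dates and show the direction and kind of error only. These are two of twelve endpoints in an exploratory study whose p-values SAP 11 treats as descriptive, so a correction of wording is enough.

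**What to change.** Before unblinding:

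1. In SAP 11.7 and 11.9, replace definition (2) with: the sum, over all ICU (hospital) stays, of the time from the later of first IP administration and admission to the earliest of discharge, death, withdrawal, end of study, database lock, or 90 days after first IP administration, including a stay open at infusion and any readmission. Word the limit as 90 days after first IP administration, because Day 90 is only 89 elapsed days.
2. Name this the main definition and keep definition (1) as descriptive.
3. In the same edit, change the continuous-outcome imputation in rules (2) to (5) of 11.7, and as carried to 11.9, so that it equals this accrued sum and not the total days since infusion until death, withdrawal, end of study or lock. Leave the time-to-event censoring dates as they are.
4. Minor: in 11.6, replace the reference to the last hospitalization with the first ICU discharge after start of treatment, to match SAP 3.2.

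The cost is SAP wording and derivation code. The infusion date (EX) and the admission and discharge dates (AEHO) are already collected.

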11.10 Severity of Acute Respiratory Distress Syndrome (ARDS)

Severity of ARDS as defined by the Berlin criteria, absolute values and changes from start of treatment (Day 1), and at Days 2, 3, 7, 15, 30, 60, 90. The categories of the ARDS severity are 0=none, 1=mild, 2=moderate, and 3=severe.

Since there are 4 categories of ARDS severity score and those categories are ordinal in nature (higher score correlates to a higher severity level) it is possible to analyze this endpoint as a continuous scale variable. The mean change in the ARDS severity score at each timepoint will be compared between treatment groups using a MMRM analysis as described above (see Section 11.2).

11.11 Cytokines and Biomarkers

Cytokine tests will be analyzed using a MMRM as described above (see Section 11.2). This is also referred to in Section 12.5 (Clinical Laboratory Tests) of this SAP.

Additionally, to better understand the underlying mechanism of action of clinical measures, correlations between biomarkers and clinical measures will be performed on CFB values within visit as well as across visits using a Spearman's correlation for continuous markers and Wilcoxon/Kruskal-Wallis Tests.

Each model described for the several clinical outcomes will also be rerun but with the addition of the biomarker as a covariate in the regression. The contribution of the biomarker will be assessed prior to that of the treatment arm using a Type I sum of squares. If a previously significant treatment effect is no longer significant and the biomarker term is significant, this provides evidence of association between the biomarker and the treatment effect of the clinical outcome. Biomarkers tend to be better powered than clinical outcomes. Consequently, a trend on a clinical outcome that is supported by a significant biomarker effect as per the model described above would also provide evidence of a treatment benefit.

Dimensionality reduction techniques, such as principle component analysis or clustering, may also be employed in order to group similar or different biomarkers together in a consistent way.

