11.2 Ordinal Scale of Clinical Improvement

Since there are 9 categories of the WHO Ordinal Scale of Clinical Improvement and these categories are ordinal in nature (higher score correlates to a higher severity level) it is possible to analyze this endpoint as a continuous scale variable.

The mean change in the WHO Ordinal Scale of Clinical Improvement at each timepoint will be compared between treatment groups using a mixed model with repeated measures (MMRM), with baseline score and weighted COVID severity risk score as covariates. Due to the small sample size and unknown variances for the two independent treatment groups, a test for equal variances and normality will be applied prior to choosing the inferential

statistical method to employ. If the test for equal variances and normality is > 0.10 (indicating that the variances are not significantly different and the data is close to normally distributed) the parametric MMRM will be used to test for treatment group differences. If the test for equal variances or normality is ≤ 0.10 (indicating that the variances are significantly different, or the data is non-normally distributed) then a non-parametric MMRM will be used.

The model will test the null hypothesis that the differences in least-square (LS) means between the active and placebo groups over 90 days is equal to zero. LS means will be estimated at each visit along with treatment differences, p-values, 95% confidence intervals for the difference in LS means, and an effect size based upon Cohen's D will be provided for treatment comparisons.

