12.5 Clinical Laboratory Tests

Safety laboratory assessments will be conducted on as specified in Schedule of Assessments (Section 18) and will be collected at Screening, Day 1 (pre-infusion), Day 2, 3, 7, 15, and 30. Assessments at Days 7, 15, and 30 will be conducted in the inpatient setting only if the subject is still hospitalized for this visit. The clinical laboratory assessments include:

- Hematology, Complete blood count with differentials. Specific laboratory tests include WBC, RBC, Hemoglobin, Hematocrit, Platelet Count, % Neutrophils, % Lymphocytes, % Monocytes, % Eosinophils, % Basophils, Absolute Neutrophils, Absolute Lymphocytes, Absolute Monocytes, Absolute Eosinophils, Absolute

Basophils.

- Chemistry. Specific laboratory tests include Sodium, Potassium, Chloride, Calcium, Bicarbonate (Total CO₂), Glucose, Blood Urea Nitrogen (BUN), Creatinine, Total Protein, Total Bilirubin, Albumin, Alkaline Phosphatase, AST / SGOT, ALT / SGPT.
- Lipid profile. Specific laboratory tests include Total Cholesterol, High-Density Lipoprotein (HDL), Triglycerides, Calculated Low-Density Lipoprotein (LDL).
- SARS-COV-2: SARS-COV 2 RT PCR (positive / negative response) at Screening and any Unscheduled.
- Inflammatory markers (i.e., Other Clinical Laboratory Assessments) to include Troponin I, Myoglobin (serum), Procalcitonin, C-Reactive Protein, Ferritin.
- Anti-inflammatory markers (i.e., Cytokine Assay) to include IL-1, IL-6, TNF alpha, IFN- γ , IL-10.
- Tryptase: taken only at unscheduled as needed within 3 hours of onset of allergic signs and symptoms.

For laboratory analysis, baseline will be defined as the closest visit prior to the administration of study treatment (Day 1 Assessments to occur prior to first infusion). Extra measurements (such as unscheduled or repeat assessments) will not be included in the descriptive statistics but will be included in subject listings.

The clinical laboratory test results measured on a quantitative scale will be summarized in a descriptive manner by calculating the mean, standard deviation, median, and range (min/max) at each visit/timepoint. The mean change from baseline (defined as Treatment 1 pre-infusion) will also be calculated and presented.

For the clinical laboratory tests that are on a qualitative scale (SARS-COV-2), and tests that are only collected at “unscheduled as needed” per the protocol (Tryptase) will be presented in the subject listings.

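### SAP 11.11 infers a biomarker link from two models that need not share the same records, so a treatment effect can lose significance through lost data alone

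*SAP*

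**What the plan says.** SAP 11.11 aims to clarify mechanism of action. Each clinical model "will also be rerun but with the addition of the biomarker as a covariate in the regression", and on the order of terms: "The contribution of the biomarker will be assessed prior to that of the treatment arm using a Type I sum of squares". The inference rule follows: "If a previously significant treatment effect is no longer significant and the biomarker term is significant, this provides evidence of association" (that is, a link from the marker to what treatment does to the outcome). The section does not say whether the covariate is a baseline value, a change at one fixed day, or a visit-matched value. Change from baseline is named only for the separate correlations, which "will be performed on CFB values within visit as well as across visits". Nothing asks for the first model to be refitted on the records that have a biomarker.

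SAP 12.5 gives the sampling. Laboratory markers and cytokines "will be collected at Screening, Day 1 (pre-infusion), Day 2, 3, 7, 15, and 30", and "Assessments at Days 7, 15, and 30 will be conducted in the inpatient setting only if the subject is still hospitalized for this visit". The ordinal scale is scheduled through Day 90 without that inpatient restriction (Protocol 1.3), with telephone follow-up after discharge. The SAP 11.2 model tests whether "the differences in least-square (LS) means between the active and placebo groups over 90 days is equal to zero", and the SAP 11.4 AUC also runs to Day 90. SAP 9.4 imputes nothing apart from listed exceptions, none of which covers biomarkers.

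**The concern.** The rule compares p-values from two fits. If the second fit has fewer records, its treatment p-value tends to rise for that reason alone, whatever the biomarker does. The second condition, a significant biomarker term, does not guard against this. A marker that predicts outcome but is unaffected by treatment will often be significant. Both conditions can then hold with no link between the marker and the treatment effect. Crossing a significance threshold also does not measure how much of the effect the marker carries.

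At stake is which markers are credited with a mechanistic role and carried into further studies.

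**Working it through.** The documents give no power, effect size, discharge rate or biomarker missingness, and the 60 subjects do not come from a formal calculation (SAP 4). So there is no plan figure to reproduce.

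**Inputs from the documents:** about 30 per arm (SAP 4); seven post-baseline ordinal visits, Days 2, 3, 7, 15, 30, 60 and 90; five post-baseline biomarker days, 2, 3, 7, 15 and 30, the last three for inpatients only.

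**Assumptions:** two-sided 0.05; a true effect giving 80% power at 30 per arm; a biomarker independent of treatment; the missing fractions, correlations and discharge rates given below.

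**Step 1, visits.** A visit-matched biomarker covers at most 5/7 = 71% of ordinal visits, and only 2/7 = 29% irrespective of discharge. A baseline value keeps 7/7.

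**Step 2, records kept.** If 20%, 50% and 75% are discharged by Days 7, 15 and 30, the fraction kept is (2 + 0.80 + 0.50 + 0.25)/7 = 0.507. With 40%, 70% and 90% it is (2 + 0.60 + 0.30 + 0.10)/7 = 0.429.

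**Step 3, power if whole subjects are lost.** The standardized effect is d = (1.960 + 0.842) × √(2/30) = 0.723, and power is Φ(d√(n/2) − 1.960). At n = 30, 24, 21, 18 and 15 per arm this gives 80%, 71%, 65%, 58% and 51%.

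**Step 4, subject-level simulation.** One outcome per subject, linear regression, 6,000 trials per setting, biomarker-outcome correlation 0, 0.3 or 0.5, subjects missing at random. Percentages are of trials whose first model was significant:

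| Subjects with biomarker | Significance lost | Full rule fires |
|---|---|---|
| 100% | 2.0-2.8% | 0.3-2.2% |
| 85% | 6.8-13.9% | 0.7-6.5% |
| 70% | 15.4-25.3% | 0.9-14.2% |
| 50% | 31.9-44.1% | 2.3-24.5% |

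With a more prognostic marker (correlation 0.4 to 0.6, effect 0.73 SD, runs of 2,000 and 4,000 trials per setting), the full rule fires in 1-2% with none missing, 11-13% at 30% missing and 20-26% at 50%. Fitting both models to the same subjects brings the last two to about 3-5% and 5-9%. If the sicker subjects are the ones retained, which is closer to how discharge works, it fires in 19% at 30% missing and 23-33% at 50%.

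**Step 5, repeated-measures simulation.** Seven visits, compound symmetry with known variance, intraclass correlation 0.3 or 0.6, the discharge rates of Step 2, 1,500 trials per setting. With a visit-matched biomarker, significance is lost in 7-21% and the full rule fires in 2-9%. With a baseline biomarker and all records kept, significance is lost in 5.5-6.0% and the rule fires in 5.5-5.8%.

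The two firing rates in Step 5 are not like for like. The visit-matched marker carried extra visit-level noise, so its term reached significance less often. The loss-of-significance rates show the effect of missing records more directly. Holding the variance fixed also withholds the precision that a prognostic covariate normally adds.

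**The case against.** A reader might infer that the rerun must have fewer subjects and visits, so that significance is bound to be lost. The documents do not support that.

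- The covariate is undefined. A baseline value is scheduled for every treated subject and costs no records by design; Days 2 and 3 are not limited to inpatients.
- In the repeated-measures models, subjects with early samples stay in, so records are lost rather than subjects. Whole-subject loss needs a single Day 7 or later covariate, for example in the AUC or Cox models, and the SAP does not say it will use one.
- Significance was lost in a minority of trials in every setting of the table and of Step 5 (at most 44%).

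Those points stand. They limit the claim but do not rescue the rule. A baseline marker precedes dosing and cannot carry a treatment effect, so the stated purpose calls for post-dose values, which is where data can be lost.

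Two further defences carry some weight. SAP 11.11 also tests treatment on each cytokine by MMRM, where an unaffected marker would usually show nothing; but the rule does not require that result. SAP 11 makes p-values descriptive, and 11.11 claims only association, so it would be too strong to say that the trial's mechanistic conclusion rests on this rule. Even so, 11.11 attaches a conclusion to crossing the threshold, and it adds that a clinical trend backed by a significant biomarker in this model would also be evidence of benefit.

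**Conclusion.** The concern holds in this form: the biomarker value is undefined, a same-records comparison is not required, and under the sampling schedule a visit-matched or Day 7 or later biomarker can make the treatment effect lose significance through lost data. A prognostic marker untouched by treatment can then satisfy the rule.

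The illustrative size is modest for the visit-matched repeated-measures model (about 2-9%, not clearly above the complete-data figure in that set-up). It is larger if whole subjects drop out (11-13% at 30% missing, 20-26% at 50%). All rates are conditional on a significant first model and rest on assumed effects, correlations and missing fractions. The main simulations took missingness as unrelated to outcome. The linear simulations stand in for the AUC case; false firing in the Cox models was not simulated.

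The clinical comparisons themselves are unaffected. The wording should be changed before unblinding.

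**What to change.** Drop the loss-of-significance rule and replace it as follows.

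1. Pre-set one post-dose biomarker term: the change at Day 2 or at Day 3.
2. Fit the models with and without it to the same subjects and visits. This is still needed, because a few early samples may be missing.
3. For linear outcomes (ordinal scale, ARDS score, AUC), report the attenuation of the treatment coefficient toward zero with a bootstrap 95% CI. Claim a link only if the interval excludes zero in the direction of attenuation and treatment also affects that biomarker in the 11.11 MMRM.
4. For Cox models, report the change descriptively and infer no link from it. Cox coefficients are non-collapsible: in simulation, a purely prognostic marker unrelated to treatment moved the treatment log hazard ratio away from zero by 0.14 to 0.37 on average.

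Both conditions in item 3 matter. An interval-excludes-zero rule alone fired falsely in 3-8% of linear-model simulations, against 1-4% for the SAP rule kept on the same subjects. The combined rule has not been simulated and should be before adoption.

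The cost is SAP wording and a bootstrap, with no new data. The small downside is that later biomarker changes become descriptive only.

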11. EFFICACY ANALYSIS

The modified Intent-to-Treat Population (as Treated) is defined as all enrolled and randomized subjects who received any amount of study treatment; the mITT population will be utilized for all efficacy analyses. All summary tables will be displayed by treatment arm.

This is a Phase 2 proof of concept study, so a hierarchical testing order will be specified, but p-values will be utilized for descriptive purposes even if a step in the hierarchy is not met and there will be no adjustment for multiplicity of analyses. In addition to the analysis by severity of COVID risk at baseline, additional subgroup analyses will be conducted on an ad-hoc basis and will be fully described in the clinical study report.

The primary analysis for each efficacy endpoint will be as follows, unless otherwise noted in the corresponding section. A Cox Proportional Hazards (PH) model will be utilized to characterize overall survival or time-to-event, correcting for baseline COVID severity risk score. This risk score will be calculated based on historical data and will include baseline characteristics of age, weight, sex, and presence of comorbidities. In addition, unadjusted Kaplan-Meier curves will be presented by treatment group and summary statistics will include estimates of median survival (and corresponding 95% confidence interval), minimum and maximum time, and the number of censored subjects. The overall survival time will be compared between the treatment arms using a log-rank test.

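### SAP 11.11, as written, lets a marker that merely tracks outcome turn a clinical trend into evidence of benefit; delete the sentence or tie it to a between-arm comparison of the marker

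*SAP*

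**What the plan says.** SAP 11.11 contains three things that matter here.

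- It opens by planning a between-arm MMRM for the cytokine tests, of the kind set out in 11.2. That model tests for a difference in least-square means between active and placebo.
- It then reruns each clinical-outcome model with the biomarker as an extra covariate: "The contribution of the biomarker will be assessed prior to that of the treatment arm using a Type I sum of squares". If a treatment effect that had been significant is lost and the biomarker term is significant, this is taken to show an association between the biomarker and the treatment effect.
- It continues: "Biomarkers tend to be better powered than clinical outcomes". From this it concludes that "a trend on a clinical outcome that is supported by a significant biomarker effect as per the model described above would also provide evidence", meaning evidence that the treatment works.

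The section does not define a trend, name a marker or visit, or require the marker to move in a favourable direction.

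The clinical models already carry baseline adjustment. The MMRM in 11.2 is fitted "with baseline score and weighted COVID severity risk score as covariates", and the Cox model in SAP 11 is fitted "correcting for baseline COVID severity risk score". SAP 11 also says that "p-values will be utilized for descriptive purposes even if a step in the hierarchy is not met", with no multiplicity adjustment. SAP 9.3 judges proof of concept on the totality of evidence across endpoints.

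**The concern.** A claim that a marker supports a drug effect needs the drug to have changed the marker. In the rerun, the biomarker is tested before arm enters the model. Inflammatory and cardiac-injury markers may well track outcome in severe COVID-19 whatever the treatment. Such a marker would meet the SAP's condition in a trial where CAP-1002 does nothing, and a chance clinical trend could then be reported as evidence of benefit.

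The trial has up to 60 subjects and no formal sample-size calculation (SAP 4), so non-significant trends are likely to be discussed. A prespecified sentence that says how to read them will carry weight in the totality-of-evidence judgement.

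**Working it through.** **1. What each model tests**

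| | Cytokine MMRM (start of 11.11) | Covariate rerun (later in 11.11) |
|---|---|---|
| Response | Marker | Clinical outcome |
| Term in question | Treatment arm | Biomarker, entered before arm |
| Null hypothesis | No difference between arms in the marker | No association of marker with outcome, given the covariates |
| Informs on drug effect on the marker? | Yes | No |

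In the rerun, outcome = covariates + marker + arm. The Type I sum of squares for the marker is its contribution given the covariates, before arm enters. If the drug affects neither marker nor outcome, the chance that this term is significant depends on the sample size and on the partial correlation r between marker and outcome.

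**2. Inputs**

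- From the documents: 60 subjects, about 30 per arm, 1:1 (SAP 4 and 5); baseline covariates in the clinical models (SAP 11 and 11.2).
- Assumed, because the documents do not give them: two-sided 0.05; a trend is a favourable result with two-sided p<0.10 or p<0.20; r from 0 to 0.4; normal data; one visit; a linear model.

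There is no figure in the plan to reproduce.

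**3. How often the marker term is significant with no drug effect (S)**

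Fisher z with one covariate: S ≈ Φ(atanh(r)·√(60−1−3) − 1.96), plus the small opposite tail. For r = 0.3: 0.3095 × 7.483 = 2.316, and Φ(0.356) = 64%. The other values of r give 12%, 33% and 89% for 0.1, 0.2 and 0.4. Simulation (100,000 null trials per value) gives the same.

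**4. False favourable call**

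This is a favourable p<0.05, or a favourable trend plus support. If support is roughly independent of the trend:

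- trend p<0.10: 2.5% + 2.5% × S
- trend p<0.20: 2.5% + 7.5% × S

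| Partial correlation | S | p<0.10: formula / simulated | p<0.20: formula / simulated |
|---|---|---|---|
| 0 | 5% | 2.6 / 2.7% | 2.9 / 2.9% |
| 0.1 | 12% | 2.8 / 2.9% | 3.4 / 3.5% |
| 0.2 | 33% | 3.3 / 3.3% | 5.0 / 4.9% |
| 0.3 | 64% | 4.1 / 4.1% | 7.3 / 7.2% |
| 0.4 | 89% | 4.7 / 4.8% | 9.2 / 9.2% |

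The reference is 2.5%.

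**5. From raw to partial correlation**

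With one severity covariate correlated 0.4 with both marker and outcome, r = (raw − 0.16)/(1 − 0.16). Raw correlations of 0.2/0.3/0.4/0.5 become 0.05/0.17/0.29/0.40. At these values about 7/25/61/90% of chance trends (p from 0.05 to 0.10) are passed as supported.

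**6. The same trials under the repaired rule**

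If support requires a favourable between-arm difference in one marker at p<0.05, 3–8% of those chance trends pass. The false call is 2.6–2.7% (p<0.10) or 2.7–3.0% (p<0.20).

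**7. Direction**

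Suppose the active arm worsens the marker by 0.5 SD with no effect on outcome (raw correlation 0.5). The rule as written still passes 76% of chance trends. The repaired rule passes 0.1%.

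**The case against.** **The authors may have meant a drug effect on the marker.** The remark about power makes sense only for a between-arm comparison, and 11.11 opens with one for cytokines. On that reading the fault is a loose cross-reference. This is plausible, and a reader should not infer that the SAP deliberately adopts an invalid rule. But the sentence points to the model above it, and the nearest one is the rerun. The MMRM reading also covers only the five cytokines. For troponin I, myoglobin, procalcitonin, CRP and ferritin the SAP specifies no between-arm model. It would be too strong to say that these five get descriptive summaries only, since the correlations and covariate reruns in 11.11 are written for biomarkers generally.

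**The rule may carry over both halves of the pattern.** If the trend must also disappear after adjustment, the chance trends passed in step 5 fall to about 3/12/28/48%. The false call becomes 2.5/2.7/3.2/3.7% (p<0.10) or 2.6/3.0/4.0/5.1% (p<0.20). This roughly halves the problem but does not remove it.

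**The size rests on assumptions.** This stands. Without covariates, S would be 65% at a raw correlation of 0.3 and 99% at 0.5. A reader might take those as the size of the problem, but the planned models adjust for baseline severity, so they overstate it. If the marker adds little beyond severity, the effect is negligible.

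**Nothing formal depends on the sentence.** This also stands. P-values are descriptive, and the between-arm cytokine results will be reported, so a reader could see that a cytokine had not moved.

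**Conclusion.** The point holds as a fault in an inference rule. As written, the support condition can be met by a marker that the drug did not change, or changed for the worse. That conclusion follows from the model and needs no assumed number.

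The size does need assumptions. With 60 subjects and one marker, the false favourable call is close to the 2.5% reference at a partial correlation of 0.1 (2.9% or 3.5%). It becomes clear from about 0.3 (4.1% or 7.2%, for trend cut-offs of 0.10 and 0.20). The calculation uses a single-visit linear model, not the full MMRM or Cox model.

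A reader might infer that the trial's error rate is uncontrolled or that a false success could be declared. The documents do not support that: this is an exploratory Phase 2 study with descriptive p-values, and no success criterion uses this sentence. The risk lies in how the report words a trend and how that wording enters the totality-of-evidence judgement. The wording should still be changed, because the repair is cheap and correct whichever model the authors meant.

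**What to change.** Before unblinding, delete the sentence, or replace it with:

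*A clinical trend will be described as supported by a biomarker only if the between-arm comparison of change from baseline in that biomarker (for cytokines, the MMRM in the first paragraph of this section) significantly favours CAP-1002. The biomarker term in the covariate models is exploratory association and is not evidence of treatment benefit.*

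Naming the marker and visit in advance is optional and for the sponsor to decide. Two facts bear on that choice.

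- The repaired rule was sized for one marker. If any of 5 or 10 unadjusted markers may serve, 33% or 42% of chance trends at p<0.20 would still find support (raw correlation 0.5, no covariates). Against that, a single marker at a single visit may miss an effect elsewhere.
- Later samples are selective: "Assessments at Days 7, 15, and 30 will be conducted in the inpatient setting only if the subject is still hospitalized for this visit". Day 3 blood may also be missing after early discharge, because follow-up moves to telephone (SAP 17, footnote 3). The number sampled per arm should accompany any marker comparison.

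The cost is SAP wording, the loss of a supportive claim, and one extra MMRM if a non-cytokine marker is used. No new data are needed.
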